## Protocol Synopsis

Full Title	Randomized Controlled Trial Comparing Covered and Uncovered Biliary Self Expanding Metal Stents (SEMS) for Pre-operative Drainage During Neoadjuvant Therapy in Patients with Pancreatic Cancer
Abbreviated Title	Pre-operative Biliary SEMS RCT During Neoadjuvant Therapy
Primary Objective	To demonstrate non-inferiority of Fully Covered biliary SEMS to Uncovered biliary SEMS in biliary drainage for the pre-operative management of biliary obstructive symptoms caused by pancreatic cancer in patients undergoing neoadjuvant therapy.
Devices	
Stent Type:
 
FC Arm: WallFlex Biliary RX Fully Covered Stent
 
UC Arm: WallFlex Biliary RX Uncovered Stent
 
Stent Diameter:
 
8mm or 10mm
 
Stent Length:
 
40mm, 60mm, or 80mm
 
The stent length will be selected to be such that the stent length should be long enough to cover the stricture completely but to leave sufficient length of normal bile duct for subsequent anastomosis.

Device Indication	
The WallFlex Biliary RX Fully Covered Stent is indicated for use in the palliative treatment of biliary strictures produced by malignant neoplasms, relief of malignant biliary obstruction prior to surgery, and for treatment of benign biliary strictures.
 
The WallFlex Biliary RX Uncovered Stent is indicated for use in the palliative treatment of biliary strictures produced by malignant neoplasms and relief of malignant biliary obstruction prior to surgery.

Study Design	Prospective, multi-center, randomized, post-market

Primary Endpoint	
Successful pre-operative biliary drainage defined as absence of reinterventions for the management of biliary obstructive symptoms.
 
 
• For patients undergoing surgery: from stent placement until surgery
 
• For patients transitioning to palliative management: from stent placement until transition to palliation
 

Secondary Endpoints	
 
1. Occurrence and severity of adverse events related to the stent and/or stenting procedure
 
2. Occurrence and severity of surgical complications
 
3. Occurrence and severity of peri-surgical complications (up to 30 days after surgery)
 
4. Ability to deploy the stent in a satisfactory position across the stricture (Stent Placement Success)
 
5. Improvement of biliary obstructive symptoms during stent indwell at Week 1 and Monthly until surgery or transition to palliation as applicable, compared to Baseline
 
6. Improvement of Laboratory Liver Function Tests (LFTs) until surgery for patients undergoing surgery, and at Week 1 and Monthly until transition to palliation, and at 1 year after stent placement for patients not undergoing surgery.
 
7. Biliary Reintervention rate
 
8. Ability to complete neoadjuvant therapy as intended without stent related interruptions of neoadjuvant therapy
 
9. Stent migration rate
 
10. Assessment by surgeon of interference, if any, of SEMS on time to surgery and/or success of pancreaticoduodenectomy
 
11. For patients transitioning to palliative management: Successful biliary drainage defined as absence of reinterventions for the management of biliary obstructive symptoms from stent placement to 1 year after stent placement
 

Hypothesis	
Statistical testing will be performed to determine if the rate of success when using the Fully Covered SEMS is non-inferior to the rate of success when using the Uncovered SEMS. The following hypothesis will be tested:
 $H_0: \pi_{UC} - \pi_{FC} \geq \Delta \text{ (Inferior)}$

	
Ha: <math>\pi_{UC} - \pi_{FC} < \Delta</math> (Non-inferior)
 
where <math>\pi_{FC}</math> and <math>\pi_{UC}</math> are the probabilities of having success in the WallFlex Fully Covered Stent and WallFlex Uncovered Stent arms respectively, and <math>\Delta</math> is defined as the non-inferiority margin.
 
The sample size was calculated for the test using an exact non-inferiority test. The assumed success rates for both study arms and the non-inferiority margin are guided by the following analysis of literature:
 
The success rate estimate is extracted from a full literature search which yielded nine articles (377 patients)  on the use of metal stents for pre-operative biliary drainage. The nine articles yielded a success rate estimate of 84.6% with a 95% CI of (80.5% - 87.9%).
 
Each arm is assumed to have a success rate of 80.5%. The non-inferiority margin (<math>\Delta</math>) is set at 20%. Given these assumptions a sample size of <math>51 \times 2 = 102</math> patients provide 80% power to reject the null hypothesis. If the p-value calculated for the test is below 0.05 it will be concluded that the test is significant, and that the WallFlex Fully Covered stent is non-inferior to the WallFlex Uncovered stent.
 
An additional 20% of patients will be enrolled to compensate for possible loss of patients to follow-up, giving a total sample size of 122 patients.

Planned Number of Patients	122
Planned Number of Sites	6-12
Key Inclusion Criteria	
 
1. Age 18 or older
 
2. Patient indicated for biliary metal stent placement for the treatment of jaundice and/or cholestasis
 
3. Willing and able to comply with the study procedures and provide written informed consent to participate in the study
 
4. Suspicion of pancreatic adenocarcinoma
 

	
 
5. Likely indicated for neoadjuvant treatment
 
6. Distal biliary obstruction consistent with pancreatic cancer
 
7. Location of distal biliary obstruction such that it would allow the proximal end of a stent to be positioned at least 2 cm from the hilum
 
8. Endoscopic and surgical treatment to be provided at the same institution
 

Key Exclusion Criteria	
 
1. Benign biliary strictures
 
2. Malignancy secondary to Intraductal Papillary Mucinous Neoplasm
 
3. Surgically altered anatomy where ERCP is not possible
 
4. Previous biliary drainage using a SEMS or multiple plastic stents
 
5. Contraindications for endoscopic techniques
 
6. Patients who are currently enrolled in another investigational trial that would directly interfere with the current study
 
7. Pregnancy
 

Visits	
 
• Screening
 
• Baseline
 
• Stent Placement Procedure Visit
 
• Pre-Operative Follow-Up Visit (Week 1 and Monthly until Surgery or Transition to Palliation)
 
• Biliary Reintervention Visit (as needed)
 
• Curative Intent Surgery
 
• Transition to Palliative Management Visit (as needed)
 
• Post-Operative Follow-Up Visit (30 day Post-Surgery visit)
 
• Long Term Follow-Up Visit (1 year after initial treatment for patients that have transitioned to palliation or 1 year post-stent placement for patients that have not undergone surgery or transitioned to palliation (with or without Neoadjuvant Therapy))
 

## 1. Introduction

In the United States, pancreatic cancer is the second most common digestive cancer and the fourth leading cause of death with a 5-year survival rate of only 5%. Globally, there are an estimated 216,000 new cases of pancreatic cancer annually. Pancreatic cancer, which is the most prevalent peri-ampullary cancer, is located in the head of the pancreas in approximately two thirds of cases. Patients with pancreatic cancer presenting with biliary obstruction can be stratified into patients with unresectable tumors, with borderline resectable or locally advanced tumors, or with resectable tumors. More than 70% of pancreatic cancer patients are poor candidates for surgery or are deemed unresectable; the WallFlex Biliary SEMS are currently indicated for use in these patients.

Some patients may be candidates for PD with curative intent, however, 25%-41% do not undergo PD as planned due to disease progression, evolving comorbidities, or decline in performance status during the time between diagnosis and scheduled PD. Pre-operative neoadjuvant chemo or chemoradiation therapy is increasingly considered in the treatment of patients with resectable or borderline resectable pancreatic cancer. The aim is to downsize tumors and improve the likelihood of a margin-free (R0) resection, to provide early treatment of micrometastases, and ultimately to optimize post-operative survival. In a recent report, 32 of 84 (38%) patients with borderline resectable disease underwent a PD after neoadjuvant therapy, with R0 resection achieved in 94% of patients and resulting median survival of 40 months post PD. In another report on 132 patients with resectable pancreatic cancer, it was found that combined neoadjuvant chemoradiation and PD yielded a median survival of 21 months from the time of tissue diagnosis, and at a median follow-up of 14 months 42 of 132 patients (32%) survived with no clinical or radiographic evidence of disease. The duration of neoadjuvant chemoradiation typically ranges from 2 to 7 months and tends to require a subsequent pre-operative resting and restaging period which can last up to several months.

Periampullary cancer including cancer in the head of the pancreas is associated with biliary obstructive symptoms such as jaundice at initial patient presentation in approximately 50%-70% of patients. Biliary obstruction requires biliary decompression. Indeed, if left untreated, prolonged biliary obstruction leads to coagulopathy, malabsorption and consequent progressive malnutrition, pruritus, hepatic dysfunction, recurrent attacks of cholangitis and altered bile salt metabolism. Pre-operative biliary drainage provides relief of biliary obstructive symptoms during neoadjuvant therapy and improves post PD tissue healing in response to reduced bilirubin levels. Without such pre-operative drainage patients may lose their resectable or potentially resectable status due to interruption of the neoadjuvant therapy and/or delayed scheduling of the intended PD. In addition, for patients receiving 3 to 4 months of neoadjuvant therapy, biliary drainage may be beneficial since some chemotherapeutic agents require adequate liver function and pre-operative immunosuppression can increase susceptibility to the risks of cholangitis if bile duct drainage is inadequate. If severely jaundiced patients do undergo PD, they may be at risk of significant post-operative complications such as renal failure and

sepsis. It is therefore important that pre-operative biliary drainage be provided during neoadjuvant therapy and the subsequent restaging and resting period.

Pre-operative biliary drainage has traditionally been achieved with plastic stents. However, these stents have been associated with high complication rates and relatively low success rates in pre-operative management of biliary obstruction. Plastic stents used for pre-operative drainage can occlude within a few weeks which in turn may necessitate additional pre-operative ERCPs. The use of SEMS provides a viable alternative that has been shown to be superior to plastic stents for pre-operative biliary drainage due to lower rates of occlusion, fewer episodes of cholangitis/cholestasis, fewer additional ERCPs before surgery, and longer stent patency resulting in most patients completing uninterrupted neoadjuvant chemoradiation therapy and preventing delays of surgery.

A literature review was conducted of clinical success of pre-operative biliary drainage using plastic or metal biliary stenting including all SEMS types used. Two associated meta-analyses were generated based on published reports of ratios of the number of patients experiencing clinical success in pre-operative biliary drainage without stent related complications over the total number of stented patients. A meta-analysis representing a total of 429 patients in six publications using plastic biliary stents yielded a biliary drainage success rate estimate of 45.9% [95% CI, 34.7% - 57.5%]. A meta-analysis representing a total of 377 patients in nine publications using SEMS yielded a biliary drainage success rate estimate of 84.6% [95% CI, 80.5% - 87.9%]. In patients who do ultimately undergo PD with curative intent, the SEMS is removed en-bloc inside the surgical specimen. Six of the 9 publications reporting on the use of pre-operative biliary drainage using SEMS state explicitly on the fact that SEMS do not interfere with successful PD and could be easily removed intra-operatively without complications. Some studies have reported an increased risk of post-operative wound infection, but there were no other reported increases in intra-operative or post-operative complications related to the use of SEMS. In addition, SEMS could be easily removed intra-operatively without complications.

Pre-operative biliary drainage (PBD) prior to Pancreaticoduodenectomy (PD) continues to be routine in many centers despite retrospective data showing that PBD increases post-operative wound infection. It was shown that these post-operative wound infections were classified on a grading scale of 1-5, with all reported occurrences rated as either 1 (oral medication and bedside intervention) or 2 (IV medication, TPN, enteral nutrition, or blood), and managed non-invasively. Other studies have also reported an increase in post-operative wound infection in the PBD group, but have indicated that although there is an increase in length of hospitalization, the length of time under anesthesia, amount of blood loss, and transfusion requirements were unaffected.

In line with the findings summarized above, SEMS have emerged as an alternative to using plastic stents for pre-operative biliary drainage. Several opinion-leading centers in this field have adopted SEMS drainage as their standard of practice in PD-bound patients undergoing

neoadjuvant therapy. Most recently leading cancer centers have published that the use of pre-operative biliary SEMS, and not plastic stents, in patients with resectable or potentially resectable pancreatic or periampullary cancer receiving neoadjuvant therapy is effective and safe. Boston Scientific is proposing a multi-center, randomized, prospective, post-market trial on the use of SEMS for biliary drainage in patients with pancreatic cancer undergoing neoadjuvant therapy.

## 2. Objectives

The purpose of this clinical trial is to demonstrate non-inferiority of Fully Covered biliary SEMS to Uncovered biliary SEMS in biliary drainage for the pre-operative management of biliary obstructive symptoms caused by pancreatic cancer in patients undergoing neoadjuvant therapy.

## 3. Design

This is a post-market, prospective, multi-center, randomized study evaluating covered and uncovered SEMS for pre-operative management of patients with pancreatic cancer undergoing neoadjuvant therapy.

### 3.1. Scale and Duration

Patients that have gone to surgery will be followed for 30 days post-surgery. For patients that have transitioned to palliation, the Long Term Follow-Up Visit will occur one (1) year after initial treatment. Patients that have not gone to surgery and have not transitioned to palliation (with or without Neoadjuvant Therapy) will be followed up to 1 year post-stent placement. There will be 6-12 participating centers with anticipated enrollment of 122 patients.

At each investigational center, there will be one principal investigator (PI) who will be an endoscopist. Where possible at least one co-investigator should be a pancreaticobiliary surgeon.

### 3.2. Treatment Assignment

Patients will be randomized at Screening in equal proportions of 1:1 ratio between Arm 1 and Arm 2 as follows:

- Arm 1: WallFlex Biliary RX Fully Covered Stent
- Arm 2: WallFlex Biliary RX Uncovered Stent

Block randomization through an online database system will be used. Randomization will be stratified by study center.

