## 7.2. Screening – *Office Visit*

- Informed Consent
- Eligibility Criteria Assessment
- Randomization

No study-specific testing will be conducted until after the patient has signed an Informed Consent Form. A Screen Failure/Enrolled Log will be maintained in EDC by the center to document select information about candidates who signed consent.

Written Informed Consent must be obtained for all patients who are potential study candidates. Patients will be asked to sign the Informed Consent Form before any study-specific tests or procedures are performed. The Informed Consent Form is study-specific and must be approved by the study Institutional Review Board (IRB). Study personnel should explain that even if a patient agrees to participate in the study and signs an Informed Consent Form, the inclusion/exclusion criteria may demonstrate that the patient is not a suitable candidate for the study. Screening and enrollment information will be collected in the database for all patients who sign a consent form.

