## 7.3. Baseline Visit – *Office Visit*

- Demographics
- Medical history
- Collection of Weight
- Patient's overall health status
- Assessment of Biliary Obstructive Symptoms
  - Right Upper Quadrant Pain
  - Fever/Chills
  - Jaundice
  - Itching
  - Dark urine
  - Pale stools
  - Nausea/Vomiting
- Laboratory Liver Function Tests (LFTs)
  - Serum Albumin level
  - Total Bilirubin
  - Alkaline Phosphatase
  - SGPT (ALT)

- Imaging

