#### **7.4. *Tumor Diagnosis, Staging, and Characteristics – Office Visit***

- Tumor Diagnosis, Staging, and Characteristics can occur any time between the Screening Visit and the Stent Placement Procedure Visit

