#### **7.5. *Planned Neoadjuvant Therapy***

- Planned Neoadjuvant Therapy can occur any time between the Screening Visit and the Stent Placement Procedure Visit

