5 ADDITIONAL DATA ANALYSES

5.1 Secondary Endpoints

1. Occurrence and severity of adverse events related to the stent and/or stenting procedure
2. Occurrence and severity of surgical complications
3. Occurrence and severity of peri-surgical complications (up to 30 days after surgery)
4. Ability to deploy the stent in satisfactory position across the stricture (Stent Placement Success)
5. Improvement of biliary obstructive symptoms during stent indwell at Week 1 and Monthly until surgery or transition to palliation as applicable, compared to Baseline
6. Improvement of Laboratory Liver Function Tests (LFTs) until surgery for patients undergoing surgery, and at Week 1 and Monthly until transition to palliation, and at 1 year after stent placement for patients not undergoing surgery
7. Biliary Reintervention rate
8. Ability to complete neoadjuvant therapy as intended without stent related interruptions of neoadjuvant therapy
9. Stent migration rate
10. Assessment by surgeon of interference, if any, of SEMS on time to surgery and/or success of pancreaticoduodenectomy
11. For patients transitioning to palliative management: Successful biliary drainage defined as absence of reinterventions for the management of biliary obstructive symptoms from stent placement to 1 year after stent placement

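### Randomisation at Screening lets the reference values for secondary endpoints 5 and 8 be recorded after the arm is known; a rule that baseline entries come first would close the gap

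*Protocol*

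**What the plan says.** Protocol 3.2 fixes the time of allocation: "Patients will be randomized at Screening in equal proportions of 1:1 ratio between Arm 1 and Arm 2". On the mechanism it adds that "Block randomization through an online database system will be used", stratified by center. Section 7.2 puts three items at the Screening visit: consent, "Eligibility Criteria Assessment" and randomisation. Table 3 marks randomisation under Screening as well.

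The entries that later serve as reference values come under other headings:

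- Section 7.3, the Baseline Visit, lists "Assessment of Biliary Obstructive Symptoms" (seven named symptoms) and "Patient's overall health status", with liver function tests and imaging.
- Section 7.4: "Tumor Diagnosis, Staging, and Characteristics can occur any time between the Screening Visit and the Stent Placement Procedure Visit".
- Section 7.5: "Planned Neoadjuvant Therapy can occur any time between the Screening Visit and the Stent Placement Procedure Visit".

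Two secondary endpoints refer back to these entries. Endpoint 5 (Protocol 4.2, SAP 5.1) is improvement of obstructive symptoms relative to the Baseline record. Endpoint 8 is "Ability to complete neoadjuvant therapy as intended without stent related interruptions of neoadjuvant therapy".

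**The concern.** A baseline value is useful because the allocation cannot have influenced it. If symptoms or the intended therapy are written down after the arm is known, that protection is lost. Expectations about one stent type could colour how pain, itching or nausea is scored before drainage, or how the therapy plan is described. The arms could then differ in apparent improvement, or in apparent completion of the plan, with no difference between the devices.

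This matters more when nobody is masked, because fixing the reference values before allocation is then one of the few protections still available. The stake is the credibility of the between-arm comparison on two secondary endpoints that rest partly on judgement.

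**Working it through.** The plan gives no figure for this point. The check sets the schedule, the safeguards and the endpoint definitions side by side.

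**Step 1. Order of events**

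| Item | Where listed | Position relative to randomisation |
|---|---|---|
| Randomisation | Protocol 3.2, 7.2, Table 3: Screening | – |
| Symptoms, health status | 7.3: Baseline Visit | Scheduled at a later visit |
| Staging | 7.4: from Screening up to stent placement | May be later |
| Planned neoadjuvant therapy | 7.5: same window | May be later |

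Table 3 marks staging and planned therapy under the Stent Placement visit, the late end of the window. No order of entries within Screening is given, and no minimum gap between Screening and Baseline.

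**Step 2. Safeguards.** Neither document describes masked assessors, delayed release of the arm, or a requirement that baseline forms be complete before allocation. The only mention of masking is generic sponsor text in Appendix B.5.2. The endoscopist does know the arm by stent placement: SAP 3.1.2 allows for an endoscopist choosing the Uncovered stent in a patient allocated to Fully Covered. Under Protocol 3.1 each site's principal investigator is an endoscopist. Who records the baseline items, and when that person learns the arm, is not stated.

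**Step 3. Which endpoints use these entries**

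- *Primary endpoint* (Protocol 4.1): absence of reintervention over a defined interval. It uses no baseline value. The sample size of 51 per arm for that test reproduces at one-sided 0.05 (exact power 80.5%) and does not depend on when randomisation takes place.
- *Endpoint 5*: uses the baseline symptom record directly. SAP 5.7 tests change from baseline.
- *Endpoint 6* (liver function tests): uses baseline, but as laboratory values.
- *Endpoint 8*: has two parts. Stent-related interruption is ascertained in follow-up. Completion as intended needs a record of intent, and the only such record in the schedule is the planned-therapy entry.

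**Step 4. Where endpoint 5 takes its first value.** Section 7.3 puts symptoms at Baseline. Table 3, as extracted from the PDF, leaves that cell empty and marks Stent Placement, yet 7.6 lists no symptom assessment at that visit. The other marks in the row agree with 7.7 and 7.9 to 7.12, which argues against a shifted row. The health-status row on the next page is visibly displaced, however, so the symptom mark should be checked against the source. Either location comes after randomisation as scheduled.

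**Step 5. Scale, by illustration only.** Planned enrolment gives 122/2 = 61 patients per arm. Let k be the number of patients in one arm whose classification changes only because the arm was known. The arm's proportion moves by k/61:

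- k = 1: 1/61 = 1.6 percentage points
- k = 3: 3/61 = 4.9 points
- k = 6: 6/61 = 9.8 points

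The documents give no basis for any value of k, and k = 0 is possible. For endpoint 5 the full shift applies to a raw change from baseline in one symptom. In a model that includes the baseline symptom as a covariate, the shift enters in proportion to that covariate's coefficient. For endpoint 8 a differently worded plan counts only if it changes that patient's classification.

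**The case against.** The strongest reply is that the documents do not show anyone recording baseline with the arm in view. Section 3.2 says how the allocation is generated, not when or to whom it is released. The windows for staging and planned therapy open at the Screening Visit, so a site could enter both before randomising. This stands. A reader might infer that baseline is written down by staff who know the arm, or that the online system discloses it at Screening. The text supports only that this can happen and that nothing prevents it.

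Several other limits also stand:

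- Only two secondary endpoints are touched. Post-procedure data are summarised descriptively (Protocol 8.4.2, SAP 5.3), and no confirmatory between-arm test is specified for endpoint 5 or 8.
- Several of the seven symptoms, such as jaundice, fever, dark urine, pale stools and vomiting, have observable signs. The list is not purely subjective.
- A reader might infer that the covariate models spread the problem further. Protocol 8.4.6 and SAP 5.6 describe optional predictor models for the primary endpoint and do not adjust endpoints 5 or 8. Only SAP 5.7 bears on endpoint 5.
- Nothing in the documents suggests that stent type would alter a therapy plan.
- Follow-up symptoms, and the attribution of an interruption to the stent, remain unmasked whatever is done about baseline.

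The reply does not supply a safeguard. The schedule still places symptoms and health status at a visit after randomisation and allows the plan of therapy to be recorded there too.

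**Conclusion.** The point holds as a gap in the plan. Randomisation is scheduled ahead of the symptom and health-status records and may precede staging and planned therapy. With no masking and no baseline-before-allocation rule, the reference values for endpoint 5 and for the as-intended part of endpoint 8 can be recorded with the arm known.

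The size of any resulting bias is unknown. The k/61 figures show only how far a given number of affected patients would move a proportion; they are not estimates. The conclusion assumes that the arm may be visible to site staff once allocated, which the documents neither state nor exclude.

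A reader might go on to infer that the trial's main result is compromised. The documents do not support that, because the primary endpoint uses no baseline value. Nor is the symptom mark in Table 3 evidence of allocation bias; it is a separate inconsistency to reconcile. The overall label is cheap improvement, low priority.

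**What to change.** 1. In Protocol 3.2, 7.2 and Table 3, state that randomisation takes place after the Baseline, staging and planned-neoadjuvant-therapy forms are entered and before stent placement. Randomising on the day of placement is not required.
2. Set the existing online system to release the arm only once those forms are complete.
3. Reconcile 7.3, 7.6 and Table 3 on the first symptom assessment, so that endpoint 5 has one reference value, taken before allocation.

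The cost is protocol wording and one check in the randomisation system. No endpoint, sample size or treatment changes. The downside is that allocation comes later, so sites have less notice of which stent is needed. Appendix B.3 says both stents are commercially available in the study regions. It does not say that sites keep them in stock, so supply should be confirmed. The change protects the reference values only, not the unmasked follow-up assessments.
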